5.2.2 Fetal Echocardiography

All patients will have standard fetal echocardiographic examinations and Doppler flow studies at the time of enrollment and then every 4 weeks (or as clinically indicated) until 37-39 weeks of gestation. The studies will be performed by two to three dedicated cardiac sonographers under direct supervision of a pediatric cardiologist. The examinations will be performed using a Siemens ACUSON Sequoia 512 ultrasound system or equivalent coupled with either a 6 C2 or an 8V3 MHz transducer (Siemens, Erlangen, Germany). Multiple two-dimensional views will be obtained to evaluate fetal heart anatomy. Doppler interrogation will be performed to evaluate valve competence, stenosis and shunting. M-mode will be used to assess cardiac rhythm. Color-flow mapping will be used to verify the anatomy, as well as intracardiac flow. The two-dimensional images will be recorded on standard video clips for subsequent analysis. Doppler samples will be obtained at the following sites: aortic valve, pulmonic valve, atrioventricular valve inflows, transverse aortic arch, ductus arteriosus, umbilical vein, DV, MCA, UA, and UtA.

For the aortic outflow, the sample volume will be placed at the level of the aortic valve on either a 5 chamber view of the fetal heart or on a long axis view of the fetal heart. For the pulmonic outflow, the sample volume will be placed at the level of the pulmonic valve on either a right ventricular outflow tract view or on a ductal view. The transverse aortic arch will be sampled on the aortic arch view while the ductus arteriosus will be sampled on the ductal view. The MCA will be sampled in the mid-portion of the vessel while the umbilical artery will be sampled in a free-floating loop. The UtA will be sampled below the crossing point of the internal iliac artery. The velocity waveforms will be obtained using an angle of insonation lower than 20°. The length of the sample volume will range between 1 and 4 mm. All recordings will be performed during periods of both fetal rest and apnea. Aortic valve diameters will be assessed from the two-dimensional images of apical five-chamber views or long axis views of the fetal heart. Pulmonic valve diameters will be assessed from the two-dimensional images of the right ventricular outflow tract view or the ductal view of the fetal heart. The measurements will be performed from video clips during systole and only the maximum diameters will be selected. Measurements will be repeated on a minimum of 3 different cardiac cycles for each valve and the values obtained will be averaged. Valvular area of the aortic and pulmonic valves will be calculated assuming a circular cross-section, according to the formula $\pi \times (\text{valve diameter}/2)^2$. The velocity time integral across both the aortic and pulmonic valve will be calculated at the area under the curve of the aortic and pulmonic outflow Doppler samples, as described above. Absolute right (RVO) and left (LVO) ventricular output (mL/min) will be derived by multiplying aortic and pulmonic valvular area, fetal heart rate and time velocity integral across the respective semilunar valve. The

combined ventricular output (CVO= RVO + LVO) and the ratio between RVO and LVO (RVO/LVO) will then be calculated.

The pulsatility index (PI) for the MCA, UA, UtA, and ductus arteriosus will be calculated according to the formula: (peak systolic velocity – end-diastolic velocity)/time-averaged mean velocity. The direction of flow in the transverse aortic arch will be recorded as all antegrade, all retrograde, or bidirectional. Any ductal constriction will be noted. A qualitative assessment of left and right ventricular cardiac function will be made. Finally, the presence or absence of hydrops fetalis will be noted.

5.2.3 Fetal Cerebral Blood Flow

MCA Flow Velocities and Pulsatility Index

Doppler color flow mapping with reduced color scale will be used to identify the circle of Willis and the MCA. Pulsed-wave Doppler will be used to determine blood flow velocities in the UA, ductus venosus (DV) and MCA. The peak systolic velocity, peak end- diastolic velocity, and time averaged mean velocity are calculated on three consecutive samples during fetal apnea, and the results averaged. The pulsatility index (PI), a measure of vascular resistance in the circulatory bed downstream from the point of Doppler sampling will be calculated according to the equation, $PI = (\text{peak systolic velocity} - \text{end diastolic velocity})/\text{time averaged mean velocity}$. The ratio of UA-PI to MCA-PI will be designated the U/C-PI ratio. PI measurements of the aforementioned vessels will be converted to gestational age-based Z-scores to allow comparisons between the treatment and control group with previously published normal values.

Fractional Moving Blood Volume

Ultrasound and power Doppler studies will be performed transabdominally, using a Phillips iU 22 (Koninklijke Phillips N.V Eindhoven, The Netherlands) ultrasound system with a C-9 MHz linear curved array transducer in the absence of fetal respiratory and body movements, and with mother and fetus in suspended respiration. The following anatomical planes of the fetal brain will be included in the pulse Doppler ultrasound color box: anterior and complete mid-sagittal, and oblique at the level of the posterior fossa. During the mid-sagittal views, special care will be taken to insonate through the sagittal suture in order to avoid the bone barrier and have an uncluttered power Doppler ultrasound recording. The size of box will be maintained as small as possible, in order to cover the different regions under investigation and to improve the frame rate. The ultrasound and power Doppler ultrasound settings to be used in all examinations will include: standard gray-scale images for obstetrics, medium persistence, high sensitivity, normal image display, pulse repetition frequency 610 Hz, medium wall filter, and gain level just below the presence of noise. The mechanical and thermal indices will always be maintained below 1. A minimum sequence of 10 consecutive good quality images without flash artifacts would be stored digitally and transferred to a personal computer for FMBV analysis in software designed specifically for the purpose. (MatLab, MathWorks, Natick, MA, USA). The regions of interest (ROI) will be defined and delimited as follows: 1) anterior cerebral, in an anterior mid sagittal view of the fetal head, delimited anteriorly by the internal wall of the skull, posteriorly by an imaginary line drawn at 90° at the level of the origin of the anterior cerebral artery and parallel to an imaginary line in the front of the face, and inferiorly by the base of the skull, 2) complete mid-cerebral, in a mid- sagittal plane delimited by the complete internal wall of the fetal skull and 3) posterior fossa, delimited anteriorly and by the base of the cerebellar hemispheres and posteriorly by the fetal skull. Each image will be rendered and the pixels containing color information within the ROI will be selected for analysis. FMBV will be calculated according to the methodology described elsewhere.^{85, 86}

5.2.4 Fetal Brain MRI

Prenatal MRI examinations will be performed once at 25-28 weeks GA and once at 34-36 weeks GA.

The prenatal MRI sequences will include:

1. T2 weighted images including half-Fourier acquisition single shot turbo spin echo T2 images in axial, sagittal, and coronal planes.
2. Echoplanar images at short and long TE to assess for hemorrhage.
3. T1 fast low angle shot images (if bleeding or clotting is suspected on other images)
4. Magnetic resonance spectroscopy.
5. Diffusion imaging.

Analysis of the fetal Brain MRI examinations will include:

1. Evaluation for anatomic abnormalities (malformations) and in-utero gross insults.
2. Size of ventricles.
3. Assessment of hemorrhage.
4. Fetal total maturation score (fTMS) evaluation which assesses myelination, cortical folding, and the germinal matrix evolution.
5. Assessment of brain volumetrics.
6. MR spectroscopic assessment of choline, N-acetylaspartate, lactate, and creatine metabolites, including corresponding ratios.

5.2.5 Post-Natal Brain MRI

Postnatal MRI examinations will include an MRI on the day of surgery and one within 10 days after surgery.

The postnatal MRI sequences will include the following:

1. T1-weighted volumetric imaging.
2. T2-weighted imaging.
3. Susceptibility weighted imaging.
4. Diffusion imaging including diffusion tensor imaging.
5. Magnetic resonance spectroscopy
6. Phase contrast flow assessment in the great vessels of the neck and superior sagittal sinus.

Analysis of the postnatal MRI will include:

1. Evaluation for anatomic abnormalities (malformations) and gross insults.
2. Qualitative and quantitative assessment of overt white matter injury (PVL).
3. Assessment of hemorrhage.
4. Postnatal total maturation score (TMS) evaluation which included assessment of cortical folding, myelination, germinal matrix evolution, and migrating bands in the frontal lobes.
5. Assessment of whole brain and segmented brain substructure volumetrics including volume of myelinated white matter (VMWM).
6. Assessment of diffusion parameters.
7. Assessment of flow in the great vessels to and from the brain by phase contrast.

8. Assessment of choline, N-acetylaspartate, lactate, and creatine metabolites, including corresponding ratios in the white matter.

5.2.6 Neurodevelopmental Evaluation

Contact Information Verification Follow-Up

After discharge from Visit 1 (post-natal hospitalization) and prior to Visit 2 (18 month follow-up), a follow-up phone call/email will be made to verify current contact information at the child's 6 month, 12 month and 15 month birthday. In addition, brochures from the CHOP patient and family education manual about child development and tips for talking will be mailed at those intervals.

The Bayley Scales of Infant Development-III (BSID-III) is an individually administered instrument that assesses the developmental functioning of infants and young children between 1 month and 42 months of age.⁶⁸ It assesses development across five domains: cognition, language, motor, social-emotional and adaptive. The cognitive, language and motor composite will be used for this study. This is the most widely used standardized developmental test battery in medical and educational settings. The composite scores have a mean of 100 and a standard deviation of 15.

The Modified Checklist for Autism in Toddlers (M-CHAT) is a brief screening instrument that was designed to detect autism in very young children. It consists of 23 yes/no items that pertain to social relatedness and communication.⁶⁹ These items were found to have the best discrimination between children diagnosed with and without autism/pervasive developmental disorder (PDD). It is an easy questionnaire for parents to complete because of its brevity and the clarity of the items. Those children who reach the cutoff should be referred for further evaluation of autism.

The Infant-Toddler Social and Emotional Assessment (ITSEA) is an empirically validated tool for identifying social-emotional problems and competencies that may be areas of concern in children 12 months to 35 months 30 days old.⁸⁷ It yields standard t-scores and percentiles in four domains with subscales and item clusters as follows: externalizing-activity/impulsivity, aggression/defiance and peer aggression, internalizing – depression/withdrawal, general anxiety, separation distress and inhibition to novelty, dysregulation-negative emotionality, sleep, eating, sensory sensitivity and Competence-compliance, attention, mastery motivation, imitation/play, empathy and prosocial peer relations. Item clusters include maladaptive, social relatedness and atypical. The ITSEA was standardized and normed based on a nationally representative sample that was stratified to match the 2002 US census.

Medical Follow-up will include obtaining growth measurements and an interim medical history followed by performance of a physical and neurological examination by a team of developmental pediatricians and a nurse practitioner.

5.3 Pharmacokinetic Evaluation

Not applicable.

5.4 Safety Evaluation

Subject safety will be monitored by adverse events, vital signs, physical examinations, and laboratory data. After randomization, participants will be instructed to contact the Investigator if any symptoms or side effects develop. In case of any events, the Investigator will initiate the appropriate treatment according to their medical judgment. Subject diaries

will also be reviewed at prenatal visits for any symptom or side effects. Recommendations for clinical intervention will be provided in the event of any unanticipated finding on brain MRI.

Recommendations for clinical intervention will be provided to any family whose child who demonstrates a developmental delay or potential genetic abnormality at the 18 month Developmental Follow-Up.

6 STATISTICAL CONSIDERATIONS

6.1 Primary Endpoint

The primary endpoint is the Motor Scale of the Bayley-III at 18 months of age.

6.2 Secondary Endpoints

Secondary endpoints will include the following:

1. Cognitive and Language Scales of the Bayley-III at 18 months of age
2. Total maturation score (TMS)
3. Volumes of whole brain, white matter, gray matter and myelinated white matter (VMWM)
4. Presence of PVL on early post-natal brain MRI (categorical y/n)
5. Presence of PVL on early post-operative brain MRI (categorical y/n)
6. PVL Volume on early post-natal brain MRI
7. PVL Volume on early post-operative brain MRI
8. Compliance with progesterone regimen
9. Compliance with pre- and post-natal MRI's
10. Failure to return for 18 month neurodevelopmental evaluation.

6.3 Statistical Methods

6.3.1 Baseline Data

Baseline and demographic characteristics will be summarized by standard descriptive summaries (e.g. means or medians and standard deviations or interquartile range for continuous variables such as age and percentages for categorical variables such as gender).

6.3.2 Efficacy Analysis

The primary analysis will be intent-to-treat and will estimate differences between group means and their associated confidence intervals. In parallel we will test the null hypothesis that treatment has no effect on each of three outcomes. Because of its clinical relevance, the study is primarily designed to provide an estimate of possible effect sizes for the Bayley-III Motor Scale at 18 months. Important information will also be provided on effect sizes for the Bayley-III Cognitive and Language Scales at 18 months, as well as total maturation score (TMS) and volume of myelinated white matter (VMWM). The analysis will use a two-sided two-sample T-interval (estimation) or T-test (hypothesis testing). The confidence level will be set at 90% and the Type I error at 10%. Normality will be assessed and a transformation, or alternatively a non-parametric test, will be used if needed.

Based on our earlier work, the occurrence of PVL, both pre- and post-operatively, has a complex distribution. At both time points, when occurrence of PVL is considered a categorical outcome, there are patients with no evidence of PVL (PVL=0), as well as patients with varying amounts of PVL (PVL=1). When occurrence of PVL is considered as a continuous variable (volume of PVL), there is a mixture distribution with a peak at zero and the remainder of

patients demonstrating a continuous highly skewed distribution. Thus it is of interest to know whether the prevalence of PVL (categorical outcome) prior to surgery and post-surgery differs between treatment groups (intention to treat). It will also be of interest to know if the volume of PVL (continuous outcome), among those who have PVL at baseline, differs between treatment groups, both at baseline and post-operatively.

In the secondary analyses, we will use an exact binomial confidence interval to estimate differences between groups in the percent of subjects with PVL pre-operatively and the rate of increase post-operatively. The null hypothesis that treatment does not reduce the frequency of occurrence of PVL pre-operatively and the rate of increase post-operatively will be tested using Fisher's Exact test. The confidence level will be set at 90% and the Type I error at 10%. The PVL data can also be modeled in a more unified approach using mixture models, where the categorical data for patients with no PVL, and the continuous data for patients with evidence of PVL are modeled jointly.⁸⁸ In addition to these analyses, we will describe compliance, both with treatment and with MRI tests, as well as determine loss to follow-up for the 18 month time point. We will secondarily model TMS, VMWM and the Bayley-III Cognitive and Language Scales as a function of treatment, as well as other potential predictors of fetal brain maturation and development including: gestational age, type of CHD, ethnicity, age at surgery, operative management variables, maternal education and socioeconomic status. Presence of 22q11 deletions or other identified genetic anomaly and apo-lipoprotein E (*APOE*) genotype will be included as covariates in the analysis of the Bayley-III scores.

6.3.3 Safety Analysis

All subjects entered into the study at will be included in the safety analysis. The frequencies of AE by type, body system, severity and relationship to study drug will be summarized for both the mother and the neonate. Serious adverse events (SAE), if any, will be described in detail.

AE incidence will be summarized along with the corresponding exact binomial 95% two-sided confidence intervals.

6.4 Sample Size and Power

Based on the formal statistical considerations described below, we plan to enroll sufficient patients to have 80 evaluable patients (40 per treatment group) at the 18 month neurodevelopmental testing. Based on known clinical outcomes for this patient population and experience with other studies with similar follow-up plans, we estimate a 5% early mortality and a further 20% attrition from all causes between hospital discharge and the 18 month evaluation. There may also be dropout prior to birth for a variety of reasons: fetal death, intolerance of therapy, withdrawal from study. We do not have accurate data to estimate this loss. We anticipate needing to enroll 110-130 patients to have a sufficient cohort at 18 months (40 per treatment group); with 60 to 52-56 patients per treatment group available for the post-natal and post-operative brain MRIs respectively.

Table 1: Expected width of confidence intervals for continuous outcomes for several possible sample sizes

N per group	Distance from Mean Difference to Limits of 90% CI based on T-interval
-------------	---

The primary goal is to provide sufficiently precise estimates of the mean difference in the 18 month Bayley-III Motor Scale to inform the design of a future pivotal trial. Secondarily we will provide estimates of differences in the TMS, VMWM, and the Bayley-III

Cognitive and Language Scales. All primary analyses will be performed on an intention-to-treat (ITT) basis.

	SD	TMS*	Bayley Score**
40	± 0.372	± 0.49	± 5.6
50	± 0.332	± 0.40	± 5.0

*based on a postulated SD=1.32

**based on a postulated SD=15 for a normalized Bayley-III Motor Scale (mean=100)

Table 1 shows that for the Bayley-III Motor Scale, assuming 40 evaluable subjects per treatment group, and an SD of 15, the $\frac{1}{2}$ width of a two-sided 90% confidence interval on the mean difference is expected to be 5.6. Thus, for example, if the mean difference is 6.0 units, a clinically relevant value for this population, the 90% two-sided confidence interval is expected to be on the order of (0.4, 11.6), suggesting that while only a minor effect cannot be ruled out, important positive effects of progesterone appear possible. In contrast, if there is no effect of progesterone we expect an interval centered around zero with i.e. (-5.6, 5.6). This initial study will thus provide important information about the magnitude of the effect of progesterone, and an indication of whether it is worthwhile to proceed with further trials. For TMS, results from [name] (personal communication) estimated the mean (median) value of TMS in a similar cohort to be 10.1 (10.0) with a standard deviation (SD) of 1.06 and range of 8.0 to 13.5. Conservatively assuming an SD that is 25% larger than that in the pilot data (SD=1.32), Table 1 shows that, with a sample size of 60 per group, two-sided 90% confidence intervals for the mean difference in TMS are anticipated to have a $\frac{1}{2}$ width on the order of ± 0.44 . Thus for TMS, if the mean difference is on the order of 2.0, the 90% confidence interval would be (1.56, 2.44). Estimated SD's for VMWM are not yet available.

Table 2: Expected endpoints of 90% confidence interval (CI) for different scenarios for PVL. Calculations are based on Pearson's Chi-square Method for n=60 (pre-surgical) or, conservatively) n=52 (post-surgical) per group.

Proportion in Control Group	Proportion in Treated Group	True Difference in Proportions	Expected Endpoints of 90% CI
Post-natal PVL (pre-surgical, n=60)			
19.0%	8.5%	10.5%	(0.3%, 20.7%)
19.0%	19.0%	0%	(-11.8%, 11.8%)
Post-operative increase in PVL from baseline (n=52)*			
38.0%	24.0%	14%	(-0.8%, 28.8%)
38.0%	38%	0%	(-14.6%, 14.6%) (-15.7%, 15.7%)
*Conservatively as we expect n=52 to 56 post-operatively			

Next we consider the categorical outcomes. In pilot data ([name], personal communication), 19% of subjects had some PVL prior to surgery and 38% of infants increased the level of

PVL post-surgery. As part of our secondary aims, the pilot study is intended to estimate the differences in these outcomes between groups. To recruit 40 evaluable subjects at 18 months we anticipate having 60 patients available pre-surgery (post-natal) and 52 to 56 after surgery. Table 2 shows that if PVL at baseline is 19% in the control group, and the true effect is 10.5%, then the endpoints of the 90% CI are (0.3%, 20.7%) This would suggest that while we could not rule out essentially a null effect of progesterone, the evidence would suggest a possible substantial effect. In contrast if there were no effect we expect the confidence interval to be centered near zero with endpoints of $\pm 11.8\%$. Similarly, if the post-operative increase in PVL is 38% in the control group, and the true effect size is 14%, then the 90% confidence interval is expected to have endpoints of the 90% CI are (-0.7%, 28.7%). Again, while we could not rule out essentially a null effect of progesterone, the evidence would suggest a possible substantial effect. In contrast if there were no effect we expect the confidence interval to be centered near zero with endpoints of $\pm 15.7\%$.

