4. Prescription or ingestion of medications known to interact with progesterone (e.g. Bromocriptine, Rifamycin, Ketoconazole or Cyclosporin)
5. Maternal use of progesterone within 30 days of enrollment
6. History of preterm birth or short cervix (defined as cervical length \leq 25 mm at 18-24 weeks GA necessitating progesterone therapy)
7. Multiple gestation
8. Maternal contraindication for MRI
9. Subjects with a known history of non-compliance with medical therapy.

Number Of Subjects	We plan to enroll sufficient patients to have 80 evaluable patients (40 per treatment group) at the 18 month neurodevelopmental testing. Based on known clinical outcomes for this patient population and experience with other studies with similar follow-up plans, we estimate a 5% early mortality and a further 20% attrition from all causes between hospital discharge and the 18 month evaluation. There may also be dropout prior to birth for a variety of reasons: fetal death, intolerance of therapy, withdrawal from study. We do not have accurate data to estimate this loss. We anticipate needing to enroll 110-130 patients to have a sufficient cohort at 18 months (50 per treatment group), with 60 and 52-56 patients, respectively, per treatment group available for the post-natal and post-operative brain MRIs.
Study Duration	The study begins during the pregnancy at 24 weeks GA and continues until the baby is 18 months of age.
Study Phases	1. Screening
Screening	2. Enrollment, baseline evaluation, randomization
Study Treatment	3. Treatment phase (24 to 39 weeks gestational age)
Follow-Up	4. Evaluation Phase (birth to 18 months of age)
Efficacy Evaluations	
 1. Motor Scale of the Bayley-III at 18 months of age. 2. Cognitive and Language Scales of the Bayley-III at 18 months of age. 3. M-CHAT and ITSEA at 18 months of age. 4. Neurological examination. 5. Total maturation score (TMS) 6. Global and regional brain volumes 7. Volume of myelinated white matter (VMWM) 8. Presence of periventricular leucomalacia (PVL) on early post-natal brain MRI (categorical y/n) 9. Presence of PVL on early post-operative brain MRI (categorical y/n) 10. PVL Volume on early post-natal brain MRI 11. PVL Volume on early post-operative brain MRI
Pharmacokinetic Evaluations	(include only if applicable)

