3.2 Allocation to Treatment Groups and Blinding

3.2.1 Randomization

The study biostatistician, [name], will generate a block randomization schedule based on stratification by fetal CHD diagnosis: TGA, HLHS, and other CHD. The randomization schedule will be based on equal allocation of subjects to the progesterone and placebo arms within each block. To ensure blinding, the randomization schedule will be generated using variable block sizes. Upon confirmation of eligibility in the DMS, the randomization module will be programmed to generate a randomization number that corresponds to a unique kit number of progesterone or placebo treatment. This kit number will be used to distribute treatment.

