3.3.2 Total Number of Study Sites/Total Number of Subjects Projected

The study will be conducted at a single site, the Children's Hospital of Philadelphia. We plan to enroll sufficient patients to have 80 evaluable patients (40 per treatment group) at the 18 month neurodevelopmental testing. Based on known clinical outcomes for this patient population and experience with other studies with similar follow-up plans, we estimate a 5% early mortality and a further 20% attrition from all causes between hospital discharge and the 18 month evaluation. There may also be dropout prior to birth for a variety of reasons: fetal death, intolerance of therapy, withdrawal from study. We do not have accurate data to estimate this loss. We anticipate needing to enroll 110-130 patients to have a sufficient cohort at 18 months (40 per treatment group), with 60 and 52-56 patients, respectively, per treatment group available for the post-natal and post-operative brain MRIs. Based on current patient

volume in the Fetal Heart Program Clinic, we anticipate there will be 70-75 eligible patients each year. If the consent rate is 65%, we will be able to complete enrollment within 3 years.

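### Protocol 6.4 misstates the TMS half-widths at 50 and 60 per group and bases pre-operative PVL precision on 60 infants per arm, which 110 enrolled cannot supply; the synopsis gives both 40 and 50 per arm at 18 months

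*Protocol*

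**What the plan says.** Protocol 6.4 justifies the sample size by the expected width of 90% intervals.

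- **TMS.** Table 1 uses SD 1.32 and prints half-widths of ±0.49 at 40 per group and ±0.40 at 50 per group. The text below it says "Table 1 shows that, with a sample size of 60 per group, two-sided 90% confidence intervals for the mean difference in TMS" have a half-width of about ±0.44, so that a difference of 2.0 would give (1.56, 2.44).
- **Numbers.** The same section says "We anticipate needing to enroll 110-130 patients to have a sufficient cohort at 18 months (40 per treatment group); with 60 to 52-56 patients" per group for the two postnatal MRIs, and later "To recruit 40 evaluable subjects at 18 months we anticipate having 60 patients available pre-surgery (post-natal) and 52 to 56 after surgery". Section 3.3.2 repeats it: "with 60 and 52-56 patients, respectively, per treatment group available for the post-natal and post-operative brain MRIs". Table 2 computes pre-operative PVL precision at 60 per group.
- **Losses.** After birth, "we estimate a 5% early mortality and a further 20% attrition from all causes between hospital discharge and the 18 month evaluation". For fetal death, intolerance and withdrawal before birth, "We do not have accurate data to estimate this loss".
- **Allocation.** Section 3.2.1: "The randomization schedule will be based on equal allocation of subjects to the progesterone and placebo arms within each block".
- **18-month target.** Sections 3.3.2, 6.4 and 9.5 say 40 per arm. The Number of Subjects row of the synopsis opens with 40 and then says "We anticipate needing to enroll 110-130 patients to have a sufficient cohort at 18 months (50 per treatment group".
- **Table 2, 38% null row.** Two intervals appear in one cell, ±14.6% and ±15.7%, under a label of 52 per group.

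**The concern.** At a fixed SD and confidence level, a larger group cannot give a wider interval, yet the protocol gives ±0.40 at 50 per group and ±0.44 at 60. At least one figure has to be wrong.

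Separately, 60 per arm is 120 infants, which is more than the lower end of the planned enrolment and leaves little room for loss at the upper end.

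The primary goal in 6.4 is an estimate precise enough to plan a later trial, so these half-widths are the design rationale. A reader relying on them would be misinformed about TMS, and would take the pre-operative PVL precision as available across the whole enrolment range when it is not.

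**Working it through.** **Inputs.** 90% two-sided two-sample t-interval (6.3.2); TMS SD 1.32, which is the pilot SD of 1.06 raised by 25%, and Bayley SD 15 (6.4); equal allocation (3.2.1); 110-130 enrolled, 5% then 20% postnatal loss, pre-operative PVL 19.0% versus 8.5% (6.4).

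**1. TMS half-width** = t(0.95, 2n-2) × SD × √(2/n)

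| n per group | SD units | Bayley (SD 15) | TMS (SD 1.32) | TMS as printed |
|---|---|---|---|---|
| 40 | 0.372 | 5.58 | 0.491 | 0.49 |
| 50 | 0.332 | 4.98 | 0.438 | 0.40 (Table 1) |
| 60 | 0.303 | 4.54 | 0.3995 | 0.44 (text) |

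The formula reproduces the whole n=40 row and the other two cells of the n=50 row (0.332 and 5.0). Only the two TMS figures fail. Table 1 contradicts itself without outside input: 0.332 × 1.32 = 0.438. With the unrounded SD, 1.06 × 1.25 = 1.325, the values are 0.440 at n=50 and 0.401 at n=60. A normal quantile gives 0.434 and 0.396. Neither variant rescues the printed figures. At n=60 a difference of 2.0 gives (1.60, 2.40).

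**2. Infants per arm**

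- 110/2 = 55 and 130/2 = 65, before any loss.
- 60 per arm needs 120 enrolled with no loss. From 130 enrolled, the tolerable loss before surgery is 1 - 120/130 = 7.7%.
- Working back from 40 at 18 months: 40/(0.95 × 0.80) = 52.6 per arm after birth. Working forward from 60: 60 × 0.95 × 0.80 = 45.6.

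**3. Pre-operative PVL**, half-width = 1.645 × √[p₁(1-p₁)/n + p₂(1-p₂)/n]

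| n per arm | 19% vs 8.5% | 19% vs 19% |
|---|---|---|
| 65 | (0.7%, 20.3%) | ±11.3% |
| 60 (Table 2) | (0.3%, 20.7%) | ±11.8% |
| 55 | (-0.2%, 21.2%) | ±12.3% |
| 53 | (-0.4%, 21.4%) | ±12.5% |
| 50 | (-0.7%, 21.7%) | ±12.9% |

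The n=60 row reproduces Table 2, so its entries are right for their label. The question is whether 60 will be available.

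**4. Synopsis target**

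- 110 × 0.76/2 = 41.8 per arm and 130 × 0.76/2 = 49.4, before prenatal loss.
- 50 per arm needs 2 × 50/0.76 = 131.6, so 132 enrolled with no prenatal loss.

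**5. 38% null row.** 1.645 × √(2 × 0.38 × 0.62/n) = 14.6% at n=60 and 15.7% at n=52. The second matches the row's label and the text of 6.4.

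**The case against.** Table 1 is visibly broken in the available text. An n=60 row may have been lost, and the printed 0.40 is exactly the n=60 value, so a cell could have been displaced. That possibility remains, but the neighbouring cells of the n=50 row are correct for n=50, and the ±0.44 and (1.56, 2.44) are running text that no table damage explains.

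The slip in the text could instead be the 60, since ±0.44 is right for 50 per group. However, TMS is read on the early postnatal MRI (2.2), and 60 is the size the protocol uses for that MRI throughout. Correcting the half-width is therefore the more natural repair.

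Sixty per arm is the midpoint of the enrolment range, is described as anticipated, and can be reached above 120 enrolled if losses are small. Having more than the 52.6 that the target requires is headroom, not in itself an error. This is fair, and it limits the point: the printed precision holds for part of the range only. The PVL limit moves by half a percentage point, and 6.4 already concedes that a null effect could not be excluded.

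The 50 in the synopsis is probably a one-figure slip, and the doubled interval in Table 2 may be struck-through text that survived extraction. Both are minor.

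**Conclusion.** The concern holds.

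- **TMS:** the n=50 entry in Table 1 overstates precision (0.40 printed, 0.44 correct). The n=60 figure in the text understates it (0.44 printed, 0.40 correct).
- **Pre-operative PVL:** the printed precision applies only from 120 enrolled upward, and then only with little or no loss before surgery. At 110 enrolled with no loss, the expected interval for 19% versus 8.5% includes zero, and the null half-width is 12.3% against 11.8%.
- **18-month target:** the synopsis contradicts itself, and its figure of 50 cannot be met within the stated enrolment.

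This rests on the protocol's own SD, interval methods, allocation and loss rates. The consequences are modest. The primary Bayley half-width (5.6 at 40 per arm) reproduces, and 110 enrolled still yields about 42 per arm before prenatal loss. The stated conclusion on PVL also stands. The figures should be corrected, but the design does not depend on them.

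**What to change.** 1. In Table 1, set the n=50 TMS entry to ±0.44 and show ±0.40 for n=60. In the text of 6.4, change the n=60 figures to ±0.40 and (1.60, 2.40).
2. Replace the single figure of 60 per arm in 6.4, 3.3.2 and the synopsis with a range that agrees with 110-130 enrolled, and show the upper half of Table 2 over it. The protocol's own figures give at most 55 to 65 per arm before any loss, and 53 as the number that the target of 40 requires. If 0-10% loss before surgery is assumed (the protocol gives no figure), the range is about 50 (110/2 × 0.90 = 49.5) to 65. The TMS half-width over 50 to 65 runs from 0.44 to 0.38.
3. Set the synopsis to 40 per arm at 18 months.
4. If ±14.6% in Table 2 is live text, delete it and keep ±15.7%.

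The cost is wording and table corrections in the protocol. No extra patients are needed, and neither the analyses nor the SAP change.
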